	
- If single value available, then use the single value for reference- If two values available, then use the average of two values for reference- If three or more values available, then use the median of the three most recent values for reference- At hospital admission (if the patient is admitted without an acute illness) 
• Patients without a reference creatinine value would also be considered to have Stage 2 or 3 AKI if they have a serum creatinine $\geq 200\%$ (≥ 2.0-fold) the normal creatinine value for age, race, and gender (Appendix F) and a renal ultrasound (US) or computed tomography (CT) showing normal kidney size within the past 90 days. Normal kidney size is defined as
- Computed Tomographic Scan
- If either kidney is ≥ 9 cm length- Renal Ultrasound⁵⁴
- <60 years if either kidney is ≥ 10 cm length- ≥ 60 years if either kidney is ≥ 9.5 cm length 
6. Study medication must be administered within 6 hours of confirmation of onset of Stage 2 or 3 AKI as established at the study site, under the following criteria
 
• After the decision is made by the attending surgeon at the study site for a surgical or interventional radiology procedure for the abdominal infection 
OR
 
• After confirmed diagnosis of abdominal infection has been established by a surgical or interventional radiology procedure 
OR
 
• After surgical confirmation of NSTI 
7. Females of childbearing potential must consistently use an acceptable method of contraception from baseline through Day 28. Females of childbearing potential must have a negative β-subunit hCG pregnancy test (urine or blood whichever is faster; blood only in France) immediately prior to study entry.
 
• Non-childbearing potential is defined as current tubal ligation, hysterectomy, or ovariectomy or post-menopause (1 year without menses with an appropriate clinical profile at the appropriate age e.g. >45 years).• Acceptable methods of contraception for this study is defined as abstinence, hormonal therapy (e.g., oral contraceptives, hormone implants), intra-uterine (IUD) device, diaphragm with spermicide, condom with spermicide. 
8. If a male patient's sexual partner is of childbearing potential, the male patient must acknowledge that they will consistently use an acceptable method of contraception (defined above) from baseline through Day 28.

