- c. Patients without a reference creatinine value would also be considered to have Stage 2 or 3 AKI if they have a serum creatinine $\geq 200\%$ (≥ 2.0 -fold) the normal creatinine value for age, race, and gender (Appendix F) and a renal ultrasound (US) or computed tomography (CT) showing normal kidney size within the past 90 days. Normal kidney size is defined as
- i. Computed Tomographic Scan
 - ii. If either kidney is ≥ 9 cm length
 - iii. Renal Ultrasound⁵⁴
 - <60 years if either kidney is ≥ 10 cm length
 - ≥ 60 years if either kidney is ≥ 9.5 cm length
6. Study medication must be administered within 6 hours of confirmation of onset of Stage 2 or 3 AKI as established at the study site, under the following criteria
- After the decision is made by the attending surgeon at the study site for a surgical or interventional radiology procedure for the abdominal infection

OR

- After confirmed diagnosis of abdominal infection has been established by a surgical or interventional radiology procedure
- OR
- After surgical confirmation of NSTI
7. Females of childbearing potential must consistently use an acceptable method of contraception from baseline through Day 28. Females of childbearing potential must have a negative β -subunit hCG pregnancy test (urine or blood whichever is faster; blood only in France) immediately prior to study entry.
 - Non-childbearing potential is defined as current tubal ligation, hysterectomy, or ovariectomy or post-menopause (1 year without menses with an appropriate clinical profile at the appropriate age e.g. >45 years).
 - Acceptable methods of contraception for this study is defined as abstinence, hormonal therapy (e.g., oral contraceptives, hormone implants), intra-uterine (IUD) device, diaphragm with spermicide, condom with spermicide.
 8. If a male patient's sexual partner is of childbearing potential, the male patient must acknowledge that they will consistently use an acceptable method of contraception (defined above) from baseline through Day 28.

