18.6 Appendix F – Twice the Serum Creatinine for Age, Race, and Gender

Age (years)	Black Males mg/dL (μmol/L)	Other Males mg/dL (μmol/L)	Black Females mg/dL (μmol/L)	Other Females mg/dL (μmol/L)
20 – 24	3.0 (266)	2.6 (230)	2.4 (212)	2.0 (166)
25 – 29	3.0 (266)	2.4 (212)	2.2 (194)	2.0 (166)
30 – 39	2.8 (248)	2.4 (212)	2.2 (194)	1.8 (160)
40 – 54	2.6 (230)	2.2 (194)	2.0 (176)	1.8 (160)
55 – 65	2.6 (230)	2.2 (194)	2.0 (176)	1.6 (142)
>65	2.4 (212)	2.0 (166)	1.8 (160)	1.6 (142)

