identical process verified through the “dummy” randomization schedule. A variable indicating the blinded treatment allocations will not be part of the clinical study data to be managed by the data management CRO to avoid risk of unblinding through inadvertent data transfer. Therefore, only blinded study data will be available to the blinded primary study statistician and blinded analysis staff. The randomization schedule parameters were set so that there would be an excess number of potential sites to over at least 60 sites in the US and at least 50 sites in France, Belgium and Netherlands. For every potential site, the maximum number of possible subjects was 30. Block sizes were randomly set to 2 or 4. Within each block, an equal number of allocations were made to the active and placebo groups. Separate randomization schedules were provided for each of 4 strata defined on the baseline of the acuity of AKI diagnosis and age category as described above.

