3.10 Creatinine, AKI, AKD, and eGFR

3.10.1 Reference Creatinine

Exhibit 1 summarizes the algorithmic determination of reference creatinine. The algorithmic determination of baseline AKI stage will be based on comparing screening creatinine to the reference creatinine determined by Exhibit 1.

Note: If there is any discrepancy between the algorithm and the assignment by the site as to reference creatinine then this will generate a medical review which may result in a modified baseline AKI stage different from the algorithmic determination. All such cases will be documented in the clinical study report. Sensitivity analyses will be conducted as needed to evaluate the impact of any modifications from the algorithmic determination.

Exhibit 1. Algorithmic Determination of Reference Creatinine		

Preprocessing step: Creatinine values obtained within 2 days of dosing will be handled as follows: If there is only one value, this value will be excluded as input to the algorithm below. If there are more than one value, compare the maximum to the minimum, and if within 25%, then all values will be included as input to the algorithm below. If greater than 25%, then the values obtained within 2 days will be excluded as input to the algorithm below.
		

This table indicates the rules to be used to determine reference creatinine based on the numbers of historical values available during the last 3 months prior to screening and available 4 to 12 months prior to screening. In general, the algorithm prioritizes use of historical creatinine values obtained within the last 3 months.
		
Number of last 3 month values	Number of 4 to 12 months	Rule
0	0	Use MDRD to determine reference creatinine.
0	1	Use the 4- to 12-month value.
0	>=2	Use median of 4 to 12 month values.
1	0	Use <= 3-month value.
>=2	>=0	Use median of <= 3-month values.
1	1	Use the mean of the two available values.
1	>=2	Use the median of all available values.
>=2	1	Use the median of all available values.

The SAS code used to implement the MDRD formula^{1,2} to determine a reference creatinine when no historical values are available is:

```

if sex='Male' and black=0 then do;
  t1 = der_age**(-0.203) ;
  t2 = 1;
  t3 = 1;
  t4 = 186 * t1 *t2 *t3 ;
  Scrt = (75 / t4 )**(-0.887) ;
end;

if sex='Female' and black=0 then do;
  t1 = der_age**(-0.203) ;
  t2 = 0.742;
  t3 = 1;
  t4 = 186 * t1 *t2 *t3 ;
  Scrt = (75 / t4 )**(-0.887) ;

```

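### Appendix F prints 2.0 mg/dL as 166 µmol/L in three cells and as 176 µmol/L in two, so the creatinine cut-off in inclusion criterion 5 depends on the unit read

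*Protocol*

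**What the plan says.** Protocol 6.1, criterion 5c, gives an eligibility route for patients with no earlier creatinine: "Patients without a reference creatinine value would also be considered to have Stage 2 or 3 AKI if they have a serum creatinine" at least 2.0-fold normal, together with imaging in the past 90 days that shows normal kidney size. The synopsis has the same rule and takes the normal value from Appendix F: "the normal creatinine value for age, race, and gender (Appendix F".

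Appendix F (protocol 18.6) is titled "Twice the Serum Creatinine for Age, Race, and Gender". Its entries are already doubled, so a site compares the patient's creatinine directly with the cell. There are 24 cells (six age bands by four race and sex columns), each with a mg/dL value and a µmol/L value in brackets. Five cells read 2.0 mg/dL:

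- Other Males over 65, Other Females 20–24 and Other Females 25–29 show 166 µmol/L.
- Black Females 40–54 and Black Females 55–65 show 176 µmol/L.

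SAP 15.2 reproduces the table with the same five entries.

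**The concern.** One mg/dL value cannot correspond to two µmol/L values, and here the conflict sits in a number that decides who may be enrolled. Protocol 9.2.8 also has sites record whether creatinine is at least 2.0-fold normal for these patients. In the three affected cells, a site working in µmol/L applies a lower bar than the criterion states, and two sites could reach opposite decisions on the same blood result. What is at stake is consistent application of one eligibility route.

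**Working it through.** **Inputs.** All 24 pairs come from protocol Appendix F and were compared with SAP 15.2. The conversion factor is the standard one for creatinine, 88.4 µmol/L per mg/dL. The documents do not state it, so the table's own implied factors (µmol/L divided by mg/dL) are shown as a check.

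**Conversion of every distinct pair.**

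| mg/dL | × 88.4 | Printed µmol/L | Cells | Printed minus converted | Implied factor |
|---|---|---|---|---|---|
| 1.6 | 141.4 | 142 | 2 | +0.6 | 88.75 |
| 1.8 | 159.1 | 160 | 3 | +0.9 | 88.89 |
| 2.0 | 176.8 | 176 | 2 | −0.8 | 88.00 |
| **2.0** | **176.8** | **166** | **3** | **−10.8** | **83.00** |
| 2.2 | 194.5 | 194 | 4 | −0.5 | 88.18 |
| 2.4 | 212.2 | 212 | 4 | −0.2 | 88.33 |
| 2.6 | 229.8 | 230 | 3 | +0.2 | 88.46 |
| 2.8 | 247.5 | 248 | 1 | +0.5 | 88.57 |
| 3.0 | 265.2 | 266 | 2 | +0.8 | 88.67 |

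The plan's figures reproduce to within 1 µmol/L in 21 of 24 cells, with implied factors from 88.0 to 88.9. The three cells at 166 do not reproduce. Rounding cannot explain them, because the same table prints 176 for the same mg/dL value.

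**Size of the error.**

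- 166 / 88.4 = 1.88 mg/dL. Over the table's own factors the range is 166 / 88.89 = 1.87 to 166 / 88.00 = 1.89.
- The implied normal value in these cells is 2.0 / 2 = 1.0 mg/dL, so the µmol/L figure sets a 1.88-fold cut-off.
- 1 − 166 / 176.8 = 6.1% below the two-fold value.
- The discordant band runs from 166 to about 176 µmol/L, which is 1.88 to just under 2.0 mg/dL.

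**Does the error carry through to SAP staging?** When there are no historical values, SAP Exhibit 1 says "Use MDRD to determine reference creatinine". The SAP code for a non-Black man is (75 / (186 × age^−0.203))^−0.887, with an extra factor of 0.742 beside the 186 for a woman.

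- Non-Black man: the reference is 1.053 mg/dL at age 66 and 1.006 at age 85. At 166 µmol/L the ratios are 1.878 / 1.053 = 1.78 and 1.878 / 1.006 = 1.87. At exactly 2.0 mg/dL they are 2.0 / 1.053 = 1.90 and 2.0 / 1.006 = 1.99. All four are below 2.0, so SAP Exhibit 2 gives Stage 1 with or without the misprint.
- Non-Black woman at 166 µmol/L: 1.91-fold at age 22, 1.98-fold at age 27 and 2.005-fold at age 29. The last is Stage 2 even at the misprinted value.

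The SAP stage therefore does not follow from the misprint.

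**The case against.** The strongest reply is that almost nothing turns on this. To be affected, a patient must have no reference creatinine, have normal kidney imaging, fall in one of three cells, be at a site that reads the µmol/L figure, and have a creatinine within about 10 µmol/L. The patient must also not qualify through urine output or planned or started RRT, which criterion 5 allows. The written rule is still 2.0-fold, and every cell prints mg/dL first. All of this stands, and it limits the point to a minor correction. It does not remove the contradiction, because both columns are offered for use. The APACHE II form (Appendix B) and the RRT guidance (protocol 9.2.11.6.1) also express creatinine in µmol/L.

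Three stronger readings are tempting, and the documents do not support them.

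- **Patients admitted through the misprint would be staged below 2 by the SAP and dropped from mITT.** The working shows otherwise: non-Black men over 65 at a correct 2.0 mg/dL are also below two-fold on the SAP fallback reference, and some women at 166 µmol/L are above it. That mismatch between Appendix F and the MDRD fallback exists independently of this error. SAP 2.3 does not say that its Stage 2 or 3 requirement means the algorithmic stage, and SAP 3.10.1 and 3.10.2 allow medical review to change the baseline stage when site and algorithm disagree on the reference.
- **The error falls on the core of the population, because men over 65 are one of the three groups.** Neither document gives an expected age or sex distribution.
- **The primary endpoint is affected.** The SAP takes missing references from MDRD, so Appendix F does not enter the eGFR calculation.

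**Conclusion.** The point holds as a small internal contradiction in an eligibility table. Three of 24 µmol/L cells are about 6% too low for the mg/dL value printed beside them and for the stated two-fold rule, and SAP 15.2 carries the same three cells. For patients in those cells with creatinine of 166 to about 176 µmol/L and no other qualifying route, eligibility depends on the unit.

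Two assumptions bear on its size. First, some sites read the µmol/L figures. The SAP's randomization lists allow for "at least 60 sites in the US and at least 50 sites in France, Belgium and Netherlands", but neither document says which unit the European laboratories report. Second, the number of patients is not given. An assumed range is 0 to 2 of 120. Treating mg/dL as the intended column is an inference, supported by the 21 consistent cells, the two cells at 176 and the wording of the criterion. No effect on the primary endpoint, power or mITT is claimed. Severity is minor.

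**What to change.** Reconcile the two unit columns in protocol Appendix F and SAP 15.2 so that the three µmol/L cells (Other Males over 65, Other Females 20–24, Other Females 25–29) agree with the printed 2.0 mg/dL and the stated 2.0-fold rule. Unit conversion gives 176–177 µmol/L, in line with the table's other two 2.0 mg/dL cells. If 166 was intended, the mg/dL entries and the criterion would have to change instead; either way the columns must agree. Send sites a short notice that names the three cells.

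The cost is three cells in each document and one memo. The cut-off becomes slightly stricter at any site that has been using the µmol/L figures.

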3. ABBREVIATIONS

Abbreviation	Description
AE	Adverse Event
AKD	Acute kidney disease
AKI	Acute kidney injury
ALP	Alkaline phosphatase
ALT	Alanine transaminase
APC	Antigen-presenting Cell
ARDS	Acute respiratory distress syndrome
AST	Aspartate transaminase
AT	As-Treated
AUC	Area under the curve
CBC	Complete blood count
CFR	Code of Federal Regulations
CHF	Congestive heart failure
CI	Confidence Interval
CKD	Chronic kidney disease
CL	Clearance (plasma)
CLSI	Clinical and Laboratory Standards Institute
CNS	Central Nervous System
COPD	Chronic obstructive pulmonary disease
CPR	Cardiopulmonary resuscitation
CRO	Contract Research Organization
CRP	C-Reactive Protein
CRRT	Chronic renal replacement therapy
CT	Computed tomography
CVVH	Continuous Veno-Venous Hemofiltration

Abbreviation	Description
DLT	Dose limiting toxicities
DPO	Data Protection Officer
EC	Ethics Committee
ECC	Endogenous creatinine clearance
ECG	Electrocardiogram
eCRF	Electronic Case Report Form
EDC	Electronic data capture
eGFR	Estimated glomerular filtration rate
FDA	US Food and Drug Administration
FiO ₂	Fraction of Inspired Oxygen
GFR	Glomerular filtration rate
GCP	Good Clinical Practice
hCG	Human Chorionic Gonadotropin
hERG	Human Ether-a-go-go Related Gene
HIPAA	Health Insurance Portability and Accountability Act
IBW	Ideal Body Weight
ICF	Informed Consent Form
ICH	International Conference on Harmonization
ICU	Intensive Care Unit
iDMC	Independent Data Monitoring Committee
IEC	Independent Ethics Committee
IgG	Immunoglobulin G
IgM	Immunoglobulin M
IHD	Intermittent hemodialysis
IMP	Investigational Medicinal Product

Abbreviation	Description
IND	Investigational New Drug
IA	Interim analysis
IRB	Institutional Review Board
ITT	Intent-to-Treat
IUD	Intra-uterine device
IV	Intravenous
KDIGO	Kidney Disease Improving Global Outcomes
KLH	Keyhole Limpet Hemocyanin
LAR	Legally acceptable representative
LOCF	Last observation carried forward
LOS	Length of stay
LPS	Lipopolysaccharide
MAR	Missing at random
MCAR	Missing completely at random
MDRD	Modification of Diet in Renal Disease
MedDRA	Medical Dictionary for Regulatory Activities
MHC	Major Histocompatibility Complex
mITT	modified Intent-to-Treat
MMRM	Mixed Model Repeated Measures
MTD	Maximum Tolerated Dose
NGAL	Neutrophil gelatinase-associated lipocalin
NOAEL	No Observed Adverse Event Level
NSAIDS	Non-steroidal anti-inflammatory drugs
NSTI	Necrotizing Soft Tissue Infection
NYHA	New York Heart Association
PAMP	Pathogen associated molecular patterns

Abbreviation	Description
PaO ₂	Partial pressure oxygen in arterial blood
PBMC	Peripheral Blood Mononuclear Cell
PE	Physical examination
PK	Pharmacokinetics
PP	Per Protocol
QTc	QT interval corrected
QTcF	QT interval corrected Fridericia
RRT	Renal replacement therapy
SAE	Serious Adverse Event
SA-AKI	Sepsis-Associated Acute Kidney Injury
SaO ₂	Arterial oxygen saturation
SAP	Statistical analysis plan
SD	Standard Deviation
SoC	Standard of Care
SOFA	Sequential Organ Failure Assessment
SOP	Standard Operating Procedure
SpO ₂	Peripheral capillary oxygen saturation
SSR	Sample size re-estimation
SUSAR	Suspected Unexpected Serious Adverse Reaction
TCR	T-cell Receptor
TEAE	Treatment Emergent Adverse Event
Th1	T-Helper 1 Cell (CD4) subset
Th2	T-Helper 2 Cell (CD4) subset
TNF	Tumor Necrosis Factor
US	Ultrasound

Abbreviation	Description
WBC	White Blood Cell
WFI	Water for Injection
WHO	World Health Organization

4. INTRODUCTION

4.1 Background Information

4.1.1 Acute Kidney Injury

AKI is a common medical condition and results in hospital complications in critically ill patients. Its incidence among intensive care unit (ICU) patients has been reported to range between 16-67%¹, and in the US it occurs in approximately 20% of hospital admissions², and according to an Australian intensive care study, it is increasing every year by 2.8%³. AKI results in an abrupt decrease in kidney function and is associated with poor prognosis, extensive morbidity, increased short term and long term mortality and significant health care expenditures⁴⁻⁷⁸. AKI is one of the most serious and common health complications, in the critical care setting (ICU), AKI is associated with a mortality rate of 60%⁹, and despite advances in supportive care, mortality rates associated with AKI remain high. Depending on AKI severity, patients spend a long time in the ICU and hospital, may require long term dialysis treatment or kidney transplantation, may develop chronic kidney disease (CKD) or end stage kidney failure and represents an important burden in clinical practice.

Any stage of AKI has implications on both short term and long term outcomes¹⁰. As was reported by Lassnigg et al. 2004, even subtle increases in serum creatinine in surgical patients were found to be associated with an augmented mortality. Even patients with transient AKI experience worse long term outcomes¹¹.

A primary driver of AKI is sepsis, especially in critically ill patients, which account for 26% of cases in developed countries¹. Clinical and basic science data indicate that sepsis-associated AKI (SA-AKI) is distinct from AKI without sepsis, based on characteristic pathophysiological mechanisms, unique profile of timing (onset and duration), and association with different short-term and long-term outcomes. Sepsis triggers a systemic cytokine-chemokine response, leading to end organ injury (which is manifested by cellular and subcellular injury: acute tubular necrosis, tubular and mesenchymal apoptosis, injury to the glomerulus, and inflammation of the nephron). Organ dysfunction secondary to sepsis is a significant contributor to mortality in critical care patients, regardless of the underlying septic cause. Furthermore, AKI can lead to inflammation and apoptosis in other organs besides the kidney, such as the lungs, heart and brain via organ cross talk¹².

With the lack of specific therapy for AKI that can either prevent AKI, hasten recovery of kidney function or abrogate the deleterious systemic effects of AKI, early detection of injury, coupled with initiation of appropriate supportive care and harm avoidance remain the mainstay of therapy.

Several components have been associated with development of AKI: inflammation, oxidative stress, apoptosis, and epithelial dysfunction. Among them inflammation has an important role, supported by evidence from both experimental models and clinical studies¹³. Following tissue injury at the site of sepsis, cells release damage associated molecular patterns (DAMPs), molecules that result in a further pro-inflammatory response

in distant organs, including the kidney through activation of immune cells (T cells and dendritic cells)¹⁴.

4.1.2 Indication

The treatment indication is SA-AKI. The Investigational Medicinal Product (IMP) Reltecimod acts as an immunomodulator to attenuate CD28 activation of T-Helper 1 Cell 1 (CD4) subset (Th1) lymphocytes. Reltecimod is being developed for the treatment of SA-AKI in conjunction with standard of care (SoC), antibiotic therapy and supportive care.

The current study, ATB-203, is a Phase 3 clinical trial that will compare efficacy and safety of Reltecimod versus placebo (both in conjunction with SoC) for the treatment of SA-AKI.

4.1.3 Investigational Medicinal Product

Reltecimod (also known as AB103 or p2TA) is the acetate salt of the synthetic peptide that consists of 10 amino acids. Reltecimod has homology to amino acid residues 8-15 of the co-stimulatory receptor CD28 and has D-Ala residues abutted to N- and C-termini to render them more protease resistant. Binding of Reltecimod to CD28 is postulated to prevent activation of CD28 by B7 on the antigen-presenting cell (APC). Reltecimod has broad spectrum activity in animal models and was shown to inhibit pro-inflammatory cytokine induction without any evidence of agonist activity (up-regulation of cytokines) in response to bacterial toxins.

Reltecimod is a lyophilized powder, formulated to contain 1 mg/mL of the Reltecimod peptide, 30 mg/mL mannitol, and 3.6 mg/mL sodium chloride after reconstitution with sterile water for injection (WFI). The drug product to be used in clinical trials will be supplied in 20 mL vials. Each vial contains nominal amounts of the API and excipients as follows: 10.5 mg of Reltecimod, 315 mg of mannitol, and 37.8 mg of sodium chloride.

Prior to use, each vial of drug (10.5 mg) is solubilized in 10.5 mL of WFI to generate a drug concentration of 1 mg/mL. 10 mL (10 mg Reltecimod) will be withdrawn from each vial and pooled together with 10 mL from additional vials, to constitute the final amount (volume) of drug needed for each patient (based on individual patient's actual body weight).

The reconstituted drug product is administered directly and is not diluted prior to administration. It will be administered at a dose of 0.50 mg/kg as an intravenous infusion given over 10 minutes.

Encouraging results from non-clinical (See Section 4.1.3.2) and clinical studies (Phase 1 and 2; see Section 4.1.3.3) indicate a good safety profile with no reported toxicities in animals or humans as well as potential efficacy in this patient population.

